In this hierarchical testing structure, each hypothesis is tested at a significance level of 0.05, two-sided. Statistical significance at each step is required in order to test the next hypothesis. If the primary endpoint meets the criteria for statistical significance, then the percent change from baseline to Week 24 in LDL-C will be tested; and so forth.

For the remaining secondary efficacy endpoints and the tertiary efficacy endpoints, a significance level of 0.05 will be used; given the large number of remaining endpoints, the p-values for those endpoints will be considered descriptive.

Percent change from baseline to Week 24 in LDL-C; change from baseline to Weeks 12 and 24 in LDL-C; percent change from baseline to Weeks 12 [REDACTED] in [REDACTED] non-HDL-C, [REDACTED] TC, apoB, and

hs-CRP will each be analyzed using ANCOVA with treatment group and patient type (primary prevention; secondary prevention) as factors and the relevant baseline as a covariate. Baseline for [REDACTED] non-HDL-C, [REDACTED] and TC will be defined as the mean of the lipid values from Week -1 (Visit S3) and predose Day 1/Week 0 (Visit T1). Baseline for apoB and hs-CRP will be defined as the predose Day 1/Week 0 (Visit T1) value. Each ANCOVA will be performed using the FAS, with patients included in their randomized treatment group regardless of the treatment they actually received. Only observed case data will be included in each analysis (no imputation will be performed for missing data). For each lipid parameter and analysis time point, the LSM and SE will be provided for both treatment groups, along with the placebo-corrected LSM, its 95% CI and associated p-value.

For all continuous efficacy endpoints (percent change from baseline in LDL-C, [REDACTED] non-HDL-C, TC, [REDACTED] apoB, and hs-CRP; change from baseline in LDL-C; to Weeks 12 and 24, as appropriate), the ANCOVA assumption of normality will be assessed. If non-normality of the data is found at any time point for any parameter, either the data will be transformed so that it is normally distributed or a nonparametric test will be used instead of the planned ANCOVA.

Additional Post-randomization Adjunctive Triglyceride-lowering Therapy:

The number and percent of patients in each treatment group requiring additional (post-randomization) TG-lowering therapy will be summarized. The medications will be summarized by treatment group.

Safety Analyses

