10.2.12. Monitoring and Management of Elevated Triglycerides

Patients may continue to use stable doses of TG-lowering medications during the study. An adjunctive therapy plan is in place for those patients whose TG values meet the protocol-defined threshold criteria. Post-randomization, TG results will be masked to investigators in order to maintain the blind; however, a threshold has been set to notify investigators and provide an opportunity to adjust the patient's standard of care regimen. Beginning at Week 4 (Visit T2), if the TG level exceeds >1000 mg/dL (11.3 mmol/L) while on treatment, the investigator will receive notification from the central laboratory that the patient has met or exceeded the protocol-defined threshold criteria for TG. The investigator will initiate the following plan:

- Any patient with TG >1000 mg/dL (11.3 mmol/L), will be reminded to fast for at least 10 hours and will return to clinic within 1 week for a repeat, fasting TG sample to confirm the TG value meets the threshold criteria
- Any patient with a confirmed TG >1000 mg/dL (11.3 mmol/L) may initiate standard-of-care therapy to lower TG using a patient-specific prescription. The initiation of this medication will be documented on the case report form as a concomitant medication with the associated start date. These medications will not be provided by the sponsor.
- Patients continuing to exceed the TG threshold after maximizing the standard-of-care triglyceride-lowering therapy will be discontinued from study drug treatment and will be asked to continue to be followed for safety using the protocol-specified visit schedule (see [Section 8.3](#)).
- Please see the Clinical Laboratory Manual for sample collection and instructions.

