Each ANCOVA will be performed using the FAS, with patients included in their randomized treatment group regardless of the treatment they actually received. Same imputation method described for the primary endpoint will be used for those secondary endpoints included in the step-down procedure, while only observed data analysis will be used for other secondary and tertiary endpoints. For each lipid parameter and analysis time point, the LSM and SE will be provided for both treatment groups, along with the placebo-corrected LSM, its 95% CI and associated p-value.

The ANCOVA assumption of normality will be assessed. If severe non-normality of the data is found at any time point for any parameter, either the data will be transformed so that it is normally distributed or a nonparametric test will be considered instead of the planned ANCOVA.

Finally, the number and percent of patients in each treatment group requiring additional (post-randomization) TG-lowering therapy will be summarized. The medications will be summarized by treatment group.

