## 16. ADDITIONAL POST-RANDOMIZATION ADJUNCTIVE LIPID-LOWERING THERAPY

The number and percent of patients in each treatment group requiring additional (post-randomization) lipid-lowering therapy will be summarized by treatment group as well as provided in a listing. The lipid-lowering therapy includes all post-randomization concomitant medications based on ATC class 2 = lipid-modifying agent.

Version Number: 1.7  
 Version Date: 21Mar2018

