### 19.4. LABORATORY EVALUATIONS

Results from the central laboratory will be included in the reporting of this study for Hematology, Blood Chemistry, Lipids, Coagulation, HbA1c, hsCRP and Urinalysis. A list of laboratory assessments to be included in the outputs is included in Protocol, [Section 10.1.6.1](#).

Presentations will use SI Units and conventional units.

Quantitative laboratory measurements reported as “< X”, i.e. below the lower limit of quantification (BLQ), or “> X”, i.e. above the upper limit of quantification (ULQ), will be converted to X for the purpose of quantitative summaries, but will be presented as recorded, i.e. as “< X” or “> X” in the listings.

The formula to calculate eGFR is:  $eGFR = 186 \times (\text{Creatinine} / 88.4)^{-1.154} \times (\text{Age})^{-0.203} \times (0.742 \text{ if female}) \times (1.210 \text{ if black})$ , where creatinine is in mmol/L.

Summaries for all lab results, including unscheduled visit values, will be included for below analyses:

- Observed and change/percent change from baseline by visit (for quantitative measurements).

[REDACTED]

Version Number: 1.7  
 Version Date: 21Mar2018

[REDACTED]

- Observed and change/percent change from baseline for HbA1c and glucose by history of diabetes and visit.
- Shift from baseline by visit according to normal ranges.
- Shift from baseline according to normal ranges for HbA1c and glucose by history of diabetes and visit.
- eGFR and values of CK will be summarized by treatment group and by baseline eGFR categories (low, normal, high).
- Potential Hy’s law cases (>3 × ULN for ALT and/or AST with concurrent Total Bilirubin >2 × ULN) will be tabulated listed.
- Laboratory abnormalities in parameters of interest

ALT or AST (> 3x ULN , >5xULN)

TB (>2x ULN)

CK (> 5x ULN) and (>10x ULN)

Fasting Blood Glucose (≤50 mg/dL, ≥126 mg/dL) by history of diabetes

HbA1c (≥6.5%) by history of diabetes

Creatinine (change from baseline for >1 mg/dL )

eGFR (< 15 mL/min/1.73m^2, 15 –< 30 mL/min/1.73m^2)

Hgb (decrease from baseline for ≥2 g/dL)

Hgb (<8 g/dL)

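### The SAP replaces the protocol's by-arm count of added triglyceride-lowering therapy with a count of any lipid-modifying agent, and has no row for triglycerides (TG) above 1000 mg/dL

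*SAP*

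**What the plan says.** The protocol synopsis, under a heading on adjunctive triglyceride-lowering therapy, states: "The number and percent of patients in each treatment group requiring additional (post-randomization) TG-lowering therapy will be summarized". Protocol 11.6 repeats the commitment and adds "The medications will be summarized by treatment group". Amendment 1 rewrote parts of 11.6 and kept both sentences (Protocol Appendix 7, Change 31).

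Protocol 10.2.12 sets the threshold. Above 1000 mg/dL the central laboratory notifies the investigator and a repeat fasting sample is taken. Then "Any patient with a confirmed TG >1000 mg/dL (11.3 mmol/L) may initiate standard-of-care therapy to lower TG using a patient-specific prescription", and at the end of the sequence "Patients continuing to exceed the TG threshold after maximizing the standard-of-care triglyceride-lowering therapy will be discontinued from study drug treatment".

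SAP 16 carries a parallel heading in which triglyceride has become lipid. It gives a by-arm number and percent plus a listing, with this scope: "The lipid-lowering therapy includes all post-randomization concomitant medications based on ATC class 2 = lipid-modifying agent".

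SAP 19.4 states "Results from the central laboratory will be included in the reporting of this study for Hematology, Blood Chemistry, Lipids, Coagulation, HbA1c, hsCRP and Urinalysis". Its list headed "Laboratory abnormalities in parameters of interest" covers ALT/AST, bilirubin, CK, fasting glucose, HbA1c, creatinine, eGFR and hemoglobin. TG is not in it.

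Protocol 11.1 lets the SAP override the protocol on data analysis.

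**The concern.** If SAP 16 is followed as written, a summary that the protocol specifies is not produced. A statin or ezetimibe added for LDL-C and a fibrate added for severe hypertriglyceridemia enter the same number. The protocol's TG action level, which can end in stopping study drug, has no frequency row, although comparable action levels do.

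Protocol 6.3 masks post-randomization TG values from sites, patients, sponsor and CRO. Apart from the notification above 1000 mg/dL, the comparison between arms depends on what the outputs tabulate. At stake is a safety description. Type I error and the efficacy hierarchy are not involved.

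**Working it through.** There is no plan figure to reproduce, so the check is mainly a comparison of texts, followed by one illustration.

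**1. Rescue count**

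| | Protocol synopsis, 11.6 | SAP 16 |
|---|---|---|
| Therapy counted | TG-lowering | any ATC level-2 lipid-modifying agent |
| Number and percent by arm | yes | yes, for the wider class only |
| Added drugs by arm | yes | not stated; a listing is given |

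The SAP gives no reason for the change. Its scope sentence also leaves open whether background therapy continuing after randomization is counted, because SAP 15 defines concomitant to include drugs ongoing at first dose.

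**2. Action levels**

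| Protocol level | Protocol section | Row in SAP 19.4 |
|---|---|---|
| ALT/AST >3x and >5x ULN, bilirubin >2x ULN | 10.2.11.3.2 | yes |
| CK >5x and >10x ULN | 10.2.11.3.3 | yes |
| eGFR 15 | 10.2.11.3.5 | yes |
| Hemoglobin fall of 2 g/dL, and <8 g/dL | 10.2.11.1 | yes |
| TG >1000 mg/dL | 10.2.12 | no |

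The INR criterion, which applies only together with raised ALT/AST, has no row either. No TG term appears in the AESI list (SAP Appendix 5), and none of the post-hoc tables in the SAP addendum concerns TG.

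**3. What the remaining outputs show**

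- SAP 15 tabulates concomitant lipid-modifying therapy separately and summarizes medications by ATC class, preferred term and arm. New starts are mixed with drugs ongoing at first dose, and fibrates and niacin are permitted background (Protocol 7.3.1). SAP 15.1 gives baseline therapy by category and arm, so comparing the two tables gives an approximate view of additions.
- The SAP 16 listing would let a reader derive new starts patient by patient.
- SAP 19.4 gives lipid values by visit and normal-range shifts. Two values above the upper limit fall in the same class whether or not they pass 1000 mg/dL. The maximum (SAP Appendix 1) shows whether anyone crossed at a visit, but not how many patients did or whether a repeat confirmed it. The one named lipid safety table, 14.3.2.10, is marked as produced for the DMC only (SAP Appendix 3).
- Under Protocol 10.1.6.4 a laboratory abnormality not already tied to an adverse event becomes one if it leads to action on study drug, needs intervention, or is judged clinically significant. It then enters the SAP 19.1 tables by preferred term, without the threshold.
- No visible output links a confirmed TG >1000 mg/dL to the therapy added for it.

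**4. Illustration of dilution**

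Inputs: n = 200 and 100 (SAP 3.1). All rates are assumed. Let r be the excess of TG rescue on bempedoic acid and q the rate of other lipid-therapy starts, equal in both arms. Then

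SE = √[(q+r)(1−q−r)/200 + q(1−q)/100], ratio = r/SE.

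| r | q = 0 (counted alone) | q = 3% | q = 5% | q = 10% |
|---|---|---|---|---|
| 1% | 1.42 | 0.46 | 0.36 | 0.27 |
| 2% | 2.02 | 0.87 | 0.71 | 0.53 |
| 5% | 3.24 | 1.95 | 1.64 | 1.28 |

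Worked for r = 2%, q = 3%: SE = √(0.05×0.95/200 + 0.03×0.97/100) = 0.0230, ratio = 0.02/0.0230 = 0.87.

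These ratios measure dilution and are not tests. A 2% rate is 4 of 200. If all 4 events fell on bempedoic acid, the exact one-sided probability under no difference is (200×199×198×197)/(300×299×298×297) = 0.196. With no events at all, the upper 97.5% limit 1 − 0.025^(1/n) is 1.8% for n = 200 and 3.6% for n = 100.

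**The case against.** A reader might infer that neither TG elevation nor its rescue can be compared by arm at all. The documents do not support that, because the outputs in step 3 of the working give partial information for both.

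A reader might also infer that the drug raises TG and that LDL-driven additions on placebo would hide it. No source is given for either part. The clinical experience in Protocol 10.2.11.1 reports no TG signal, and post-randomization LDL-C is masked to sites and patients. Counts at which the two effects cancel can be constructed, but nothing in the documents points to them.

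Four further objections have weight:

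- The protocol promises a rescue count. It does not promise a frequency table above 1000 mg/dL, so that half of the point rests on consistency with the other action levels.
- A wider definition suits the adjunctive-therapy sensitivity analysis in SAP 18.2.3.2, and Protocol 11.1 allows the SAP to differ.
- The tertiary sections are redacted and the table templates (SAP 8) are not available. Either could contain a TG analysis or a breakdown by drug.
- Entry excludes TG of 500 mg/dL or more, so the threshold is about twice the entry limit and crossings may be rare.

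These objections narrow the point and lower its weight. They do not restore the dropped summary: the SAP text names no TG-lowering subset, and the unredacted list in 19.4 has no TG row.

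**Conclusion.** The point holds in a limited form. The visible SAP text drops the protocol's by-arm count of added TG-lowering therapy and prespecifies no count of patients above the protocol's TG action level. A direct by-arm comparison of either is therefore not prespecified. Indirect comparison remains possible.

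The size cannot be estimated, because the documents give no rate for crossings or rescue. On assumed rates, merging dilutes a TG-specific difference substantially, but with few events even a dedicated row describes and does not test. The conclusion assumes that the redacted sections and the templates do not already supply these rows. The change is worth making because a safety summary that the protocol specifies is lost and restoring it is cheap.

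**What to change.** **SAP 16.** Keep the overall row, which fits the adjunctive-therapy sensitivity analysis. Add, by arm and by drug name, the subset of TG-lowering therapy started or changed after randomization. Identify it from the indication recorded for each concomitant medication (Protocol 7.3) together with ATC class. Class alone is not enough, because Protocol 10.2.12 does not specify which standard-of-care therapy is used. State that background therapy continued unchanged is not counted.

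**SAP 19.4.** Add two rows by arm: any post-baseline fasting TG >1000 mg/dL, and TG >1000 mg/dL confirmed on the repeat fasting sample. Carry both into Table 14.3.2.9.

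**Cost.** A few descriptive table rows from data the protocol already collects. No clinical rule changes. The SAP addendum records that the planned analyses have been run, so rows produced now should be labelled as a post-hoc supplement.

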## 17. STUDY MEDICATION COMPLIANCE AND EXPOSURE

Compliance to study medication will be presented for the SAF. At visits Week -1 (S1), Week 0 (T1), and each patient visit during the study, clinical site staff will count the number of tablets that are returned as unused and query the patient with regards to daily intake.

### 17.1. DERIVATIONS

Compliance with placebo-run in (as an overall group) and double-blind study medication by treatment group—based on the drug accountability data—will be calculated as the number of tablets taken (total dispensed – total returned) divided by the number of days on treatment within each of the 2 periods.

During the run-in period, the compliance will be summarized as a single overall group and during the double-blind period, compliance will be summarized by treatment group (bempedoic acid and placebo).

Compliance will not be computed by visit.

A 35-day supply of single-blind placebo drug will be dispensed one time at Week -4 (Visit S2) for the 4-week placebo run-in period of the study. Double-blind IMP will be dispensed in 100 day supply increments to patients by appropriate clinical site personnel. Patients will receive one 100-day supply bottle at Week 0 (Visit T1).

The treatment is taken once daily and it is assumed that the patient takes medication on the visit day at which their medication is initially dispensed to the date of last dose as captured on the End of Treatment eCRF page. For example, if the initial dispense date is Day 1 and the last dose is Day 84, then the patient should have taken the first tablet at Day 1, once a day on Days 2 to 83 and 1 tablet on Day 84; hence, the total number of prescribed tablets would be 84.

For subjects who did not return any bottle during the double-blind period, their compliance will be set to missing.

Treatment exposure will be calculated in weeks as (date of last dose of study medication – first date of first dose of study medication +1)/7. Descriptive statistics will be presented for exposure as well as categorization into time periods (e.g., <12weeks, >=12 weeks to <24 weeks, >=24 weeks, etc.).

[REDACTED]

Version Number: 1.7  
 Version Date: 21Mar2018

[REDACTED]

## 18. EFFICACY OUTCOMES

### 18.1. PRIMARY EFFICACY

#### 18.1.1. PRIMARY EFFICACY VARIABLE & DERIVATION

The primary efficacy endpoint is the percent change from baseline to Week 12 in LDL-C. Baseline LDL-C is defined as the mean of the LDL-C values from Week -1 (Visit S3) and predose Day 1/Week 0 (Visit T1).

In cases where triglycerides (TG) is >400 mg/dL or LDL-C is <=50 mg/dL, a measured LDL (LDL-M) will be used instead of LDL-C for the analysis of that time point. If both values are available, the LDL-M will be used.

#### 18.1.2. PRIMARY ANALYSIS OF PRIMARY EFFICACY VARIABLE

The null hypothesis,  $H_0$ , will be that there is no difference between bempedoic acid 180 mg/day and placebo in mean percent change from baseline to Week 12 in LDL-C. The alternative hypothesis,  $H_1$ , will be that bempedoic acid 180 mg/day is different from placebo:

$$H_0: \mu_p = \mu_b$$

$$H_1: \mu_p \neq \mu_b$$

where  $\mu_p$  and  $\mu_b$  denote the mean percent change from baseline to Week 12 in LDL-C on placebo and bempedoic acid 180 mg/day respectively.

The primary efficacy endpoint will be analyzed using analysis of covariance (ANCOVA), with treatment group and stratification factor patient type as factors and baseline LDL-C as a covariate. To account for the likelihood of unequal variances between the treatment groups, the ANCOVA model will be implemented within mixed model framework and the *<repeated/group=>* option will be used to allow estimating the residual variances separately between the groups. Model assumptions for performing ANCOVA will be assessed and if the assumptions are severely violated, non-parametric methods will be performed.

In addition, descriptive statistics will be presented for LDL-C at each visit and for change from baseline and % change from baseline.

**18.1.3. MISSING DATA METHODS FOR PRIMARY EFFICACY VARIABLE**

For the primary endpoint of percent change from baseline to Week 12 in LDL-C values, a pattern mixture model (PMM) will be used to specify different imputation strategies depending on whether the patient is still on study treatment. Patients with missing lipid data at Week 12 who are no longer taking study treatment (defined by date of last dose of study medication is < Week 12 lab assessment date -7) can be assumed to no longer be benefitting from study medication, and their missing value(s) can be assumed to be similar to those in placebo group who remained on study and have data. To account for uncertainty, missing values will be imputed using multiple imputation via a regression based model including stratification and baseline data from placebo subjects only. In this imputation model, treatment group will not be included as a factor.

Patients with missing lipid data at Week 12 who are still taking study treatment (date of last dose of study medication is ≥ Week 12 lab assessment date -7) can be assumed to continue to benefit from study medication, and their missing value(s) can be assumed to be similar to those who remain on study treatment and have data and as a result, lipid values will be imputed based on the observed values in their randomized treatment group at Week 12. To account for uncertainty, missing values will be imputed using multiple imputation via a regression based model including treatment, stratification and baseline value.

Imputed datasets will be analyzed using the same ANCOVA model with treatment and stratification as factors and baseline LDL-C as a covariate described in [section 18.1.2](#). Approximately 200 imputed datasets will be created, with results from the analysis of each imputed dataset combined using Rubin’s method. The least squares mean (LSM) and standard error (SE) will be provided for both treatment groups, along with the placebo-corrected LSM, its 95% confidence interval (CI) and associated p-value. To account for possibility of unequal variances between the groups, the ANCOVA model will be implemented within mixed model framework where <repeated/group=> option will be used to allow separate estimation of residual variance between the groups.

Further information on the multiple imputation method is presented in [Appendix 4](#).

